#### 4.2 Secondary outcomes

#### **Blood amino acids**

Blood samples of each volunteer will be collected at the investigators' study center at baseline and after the 3-week CR intervention. The concentrations of 31 blood amino acids and derivatives in the fasting serum samples will be measured by LC-MS/MS.

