#### 6. Analyses

All outcomes will be presented using descriptive statistics: Wilcoxon rank-sum test is used to detect the significant differences on phenotypes, the concentrations of blood amino acids and the relative abundances of genera and species between enterotypes. Wilcoxon signedrank test is used to detect the significant differences on phenotypes, the concentrations of blood amino acids and the relative abundances of genera and species in paired samples before and after the intervention. Permutational multivariate analysis of variance (PERMANOVA) is used to detect the association between enterotypes and the overall blood amino acid profile at baseline by using PERMANOVA with 9,999 permutations on enterotypes. Principal coordinate analysis is used to visual overall gut microbial based on the relative abundance profiles between baseline and after the intervention. Principal component analysis is used to visual overall amino acid composition based on the blood amino acid profiles between baseline and after the intervention. To investigate whether we could predict BMI loss ratio using omics features, we will perform a Lasso (Least absolute shrinkage and selection operator) regression analysis between baseline relative abundances of gut common species and the concentrations of blood amino acids (independent variables), and BMI loss ratio (dependent variables). We first normalize values of both independent and dependent variables (R, scale function). We then use the R function cv.glmnet to choose the most appropriate value for  $\lambda$  in the Lasso model (R glmnet package, alpha =1, family="gaussian", nfolds=10, alpha=1, nlambda=100). Here,  $\lambda$  is the tuning parameter ( $\lambda > 0$ ) which controls the strength of the shrinkage of the variables. We then apply the Lasso feature selection process by shrinking the Lasso regression coefficients of non-informative variables to zero and selecting the variables of non-zero coefficients. To reduce overfitting with a limited sample size (n=41), we apply leave-one-out cross

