validation (LOOCV) to estimate the prediction performance of BMI loss ratio using a generalized linear model (GLM) of the selected features (creatFolds function in R caret package and the glm function in R base package). Likewise, we also use baseline BMI values for LOOCV to estimate its prediction performance for CR-associated BMI loss ratio. Spearman's rho values will be calculated between actual BMI loss ratios and the predicted values. P-value adjustment is applied for multiple hypothesis testing on the concentrations of blood amino acids, the relative abundances of gut microbial genera and species use Benjamini-Hochberg (BH) method. R 3.5.0 will be used for all statistical analysis.

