# 7. Missing data

In this study, data of 5 participates' blood amino acids was missing at baseline and after the intervention. For a specific analysis, the study participates with missing data on the blood amino acids will be excluded from the analysis.

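### Lasso selection before leave-one-out inflates the omics rho, leave-one-out itself lowers the baseline-BMI rho, and no null reference is planned for either

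*SAP*

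**What the plan says.** SAP section 6, repeated in Protocol section 6.1, sets out the prediction of BMI loss ratio in this order.

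1. Scale all variables, then tune λ with cv.glmnet (10 folds, 100 values of λ). Candidate predictors are baseline amino acids and common gut species.
2. Select: "We then apply the Lasso feature selection process by shrinking the Lasso regression coefficients of non-informative variables to zero", keeping the variables with non-zero coefficients.
3. Validate: "To reduce overfitting with a limited sample size (n=41), we apply leave-one-out cross" validation, used to "estimate the prediction performance of BMI loss ratio using a generalized linear model (GLM) of the selected features".
4. Comparator: "Likewise, we also use baseline BMI values for LOOCV to estimate its prediction performance for CR-associated BMI loss ratio".
5. Measure: "Spearman's rho values will be calculated between actual BMI loss ratios and the predicted values".

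Neither document says that selection is repeated when a participant is left out. Neither gives a null value, permutation test or interval for rho, a rule for choosing λ, or a result to report if no feature survives. The Benjamini-Hochberg adjustment does not cover rho. SAP section 7 adds that "data of 5 participates' blood amino acids was missing at baseline and after the intervention", so at most 41 − 5 = 36 participants can enter a model that uses amino acids.

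**The concern.** LOOCV is offered as the guard against overfitting. As ordered, though, the held-out participant has already helped to choose the features, so the guard does not cover the step where most overfitting occurs when there are far more candidates than participants. The comparator has the reverse problem. Leaving out a high outcome lowers the training mean, so a weak model's prediction moves away from the held-out value and rho tends to be negative. Zero is therefore the wrong benchmark for both models, and wrong in opposite directions.

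At stake is any statement that omics features predict BMI loss, or predict it better than baseline BMI. Such a statement would feed directly into the stated aim of informing microbiome-based personalised nutrition.

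**Working it through.** **Plan's own figure.** None exists for rho. The only design figure is the sample size for BMI change (SAP section 2.1). It reproduces (35, power 0.801; 35/(1 − 0.30) = 50) and has no bearing on prediction.

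**Inputs from the documents.** n = 41 (SAP section 6), or 36 with amino acids (section 7); 31 amino acids (section 4.2); Lasso then LOOCV; Spearman's rho.

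**Assumptions.** 50, 100 or 200 common species, so 81, 131 or 231 candidates; the λ with the smallest cross-validated error; independent Gaussian predictors; the GLM taken as an ordinary linear model; outcome independent of every predictor unless stated.

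**Step 1: why zero is not the null.** The leave-one-out prediction is ŷ(−i) = y_i − e_i/(1 − h_i), where e_i is the residual and h_i the leverage. With an intercept only, ŷ(−i) = (nȳ − y_i)/(n − 1), which falls as y_i rises, so rho is exactly −1.

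**Step 2: pre-specified noise predictors (4,000 runs per setting).** With one predictor, as for baseline BMI, rho has mean −0.32 and median −0.25 at n = 41, and mean −0.33 and median −0.27 at n = 36; it is negative in 77% of runs at either size. At n = 41 the mean is −0.18 with 2 predictors, −0.10 with 5, −0.06 with 10 and −0.02 with 20.

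**Step 3: baseline BMI with a real association (n = 41).**

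| True r | Mean leave-one-out rho | Mean ordinary rho | Difference |
|---|---|---|---|
| 0 | −0.323 | 0.000 | −0.323 |
| 0.2 | −0.079 | 0.188 | −0.267 |
| 0.3 | 0.104 | 0.278 | −0.174 |
| 0.4 | 0.272 | 0.374 | −0.102 |
| 0.5 | 0.412 | 0.474 | −0.062 |
| 0.6 | 0.527 | 0.570 | −0.043 |

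**Step 4: the plan as written, no association anywhere (250 runs per setting).** Lasso on all data, then LOOCV of a linear model on the selected features.

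| n | Candidates | Nothing selected | Mean omics rho if selected (2.5% point) | Mean BMI rho |
|---|---|---|---|---|
| 36 | 81 | 50% | 0.64 (0.35) | −0.33 |
| 36 | 131 | 51% | 0.67 (0.36) | −0.31 |
| 36 | 231 | 44% | 0.71 (0.36) | −0.32 |
| 41 | 81 | 43% | 0.62 (0.29) | −0.30 |
| 41 | 131 | 43% | 0.63 (0.34) | −0.29 |
| 41 | 231 | 51% | 0.69 (0.35) | −0.31 |

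Where something was selected, omics exceeded BMI in about 100% of runs. The usual one-sided 5% critical value of rho is 0.279 at n = 36 and 0.260 at n = 41. In every row the 2.5% point lies above it, so at least 97.5% of null runs with a selection would pass as significant.

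**Step 5: averaging over all null runs.** An empty selection leaves an intercept-only model, with rho −1. At n = 36 with 131 candidates, 0.49 × 0.67 + 0.51 × (−1) = −0.18, against −0.31 for BMI: a gap of 0.13. At n = 36 with 231 candidates, 0.56 × 0.71 + 0.44 × (−1) = −0.04, against −0.32: a gap of 0.28. The other rows fall between these.

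**Step 6: selection repeated inside each fold** (n = 36, 131 candidates, 30 values of λ, 100 null runs). Omics rho has mean −0.36 (SE 0.05) and median −0.33, close to baseline BMI. The asymmetry largely goes, but zero is still not the null value.

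**Step 7: possible references.** For baseline BMI the upper 5% point of the null rho is 0.19 at n = 41 and 0.20 at n = 36, so the usual critical values are conservative for that model. Q2 = 1 − Σ(y_i − ŷ(−i))² / Σ(y_i − ȳ(−i))², where ȳ(−i) is the leave-one-out mean, has null mean −0.03 for baseline BMI at either n.

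**Step 8: can permuting the outcome test the difference in Q2?** Take two one-predictor models that predict equally well, both with r = 0.4. A two-sided test at nominal 5% rejected in 42% of runs (n = 36, 1,500 runs, 399 permutations); a separate check gave 44%. Permuting the outcome tests that neither model predicts, not that they predict equally.

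**The case against.** The prediction analysis is not among the primary or secondary outcomes (Protocol section 4.1, SAP section 4). No test of omics against baseline BMI, no superiority claim and no decision rule is written; the comparison is implied by running the same procedure on both. The sizes also depend on an unstated number of species, an unstated λ rule and independent Gaussian predictors. BMI loss ratio is not defined, and if it is divided by baseline BMI, independence from baseline BMI is not its natural null. All of this stands. It limits the importance of the point but does not remove the bias, which appears in every setting tried.

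Three stronger readings are tempting and are not supported.

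- A reader might infer that the leave-one-out shift is what tilts the comparison against baseline BMI. Step 6 shows otherwise: with selection nested in the folds, both models shift down about equally. The smaller shift for larger models in step 2 applies to pre-specified features, which this plan does not use.
- A reader might infer that omics must beat baseline BMI by construction, with an expected gap near 0.9. A gap of that size occurs only when Lasso selects something. In 43% to 51% of null runs it selects nothing and the order reverses; over all runs the average gap is 0.13 to 0.28.
- A reader might infer that rho can have no valid reference. None is planned, but permuting the outcome and rerunning the whole pipeline would supply one for each model.

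**Conclusion.** The point holds as a bias in reported predictive performance, with two causes of unequal weight. The main one is selection on all the data before LOOCV, which puts the null omics rho at about +0.6 to +0.7 whenever a feature is selected. The secondary one is the leave-one-out shift, which puts the null baseline-BMI rho at about −0.32 on average (median about −0.25) and shrinks to about −0.05 at true correlations of 0.5 or more. When Lasso selects something, omics will look better than baseline BMI even if neither predicts; when it selects nothing, rho is −1 and the plan does not say what is reported. The figures rest on 81 to 231 candidates, the error-minimising λ and independent Gaussian predictors. The primary outcomes are unaffected. The change should be made because it is cheap and the uncorrected figures cannot be interpreted.

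**What to change.** Amend SAP section 6 and Protocol section 6.1 as follows.

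- Repeat scaling, cv.glmnet tuning and feature selection inside each left-out fold, and state the λ rule.
- State what is reported when no feature is selected: the leave-one-out mean as the prediction, hence Q2 = 0 if this happens in every fold.
- Fit both models in the same participants, the 36 with amino acids, and correct the n given for this analysis.
- Define BMI loss ratio.
- Report the cross-validated Q2 of step 7 for each model.
- Judge each model's rho or Q2 against its own null, obtained by permuting BMI loss ratio and rerunning the whole pipeline.
- Report the difference in Q2 descriptively, with no p-value from permuting the outcome (step 8).

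The cost is SAP wording and computing time: with 1,000 permutations, for example, about 36 × 1,000 = 36,000 cv.glmnet fits. No new data are needed. Reported performance will probably be less favourable.

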# 7. Missing data

In this study, data of 5 participates' blood amino acids was missing at baseline and after the intervention. For a specific analysis, the study participates with missing data on the blood amino acids will be excluded from the analysis.

